Hepatitis B Virus (HBV):

Subjects will be tested for the presence of HBV at screening using the following tests:

[figure not shown]
- HBs Ag (Hepatitis B surface antigen)
- HBc Ab/anti-HBc (Hepatitis B core antibody)
- HBs Ab/anti-HBs (Hepatitis B surface antibody)

A positive result for HBs Ag will be exclusionary.

A negative result for HBs Ag will be tested (automatic reflex testing) for core antibodies (HBc Ab) and surface antibodies (HBs Ab).

- A negative test result for HBc Ab does **not** require HBV DNA PCR qualitative testing and the subject may be enrolled (Figure 3, Scenarios A and B). For a subject who has had a HBV vaccination (should document in the medical history), a positive test result for HBs Ab is expected and the subject may be enrolled (Figure 3, Scenario B).*
- A positive test result for HBc Ab requires HBV DNA PCR testing (automatic reflex testing) (Figure 3, Scenarios C and D).
 - A positive result for HBV DNA or a result that exceeds detection sensitivity will be exclusionary.
 - A subject with a negative result for HBV DNA may be enrolled.

Figure 3. Criteria for HBV DNA PCR Qualitative Testing

* For subjects who have had a HBV vaccination (should document in the medical history), a positive test result for HBs Ab is expected and these subjects may be enrolled.

Hepatitis C:

Blood samples for hepatitis C serology will be obtained at the Screening Visit. A subject will not be eligible for study participation if test results indicate active hepatitis C (HCV RNA detectable in any subject with anti HCV Ab).

HIV

Subjects with a known history of HIV infection are excluded from study participation. If required by country regulatory authorities to confirm eligibility, subjects should be tested for antibodies to HIV prior to Screening. This testing is to be done at a local lab. A subject will not be eligible for study participation if test results indicate a positive HIV infection. AbbVie will not receive results from the testing and will not be made aware of any positive result.

Randomization/Drug Assignment

All Screening laboratory results must be reviewed, signed and dated by the Principal Investigator or Sub-investigator prior to the Baseline Visit. Subjects will not be enrolled into the study if laboratory or other Screening result abnormalities are deemed clinically significant by the Principal Investigator or Sub-investigator.

Subjects will be eligible for randomization if they continue to meet all of the selection criteria (Section 5.2) at Baseline and are willing to continue in the study.

Subjects will be randomized in a 2:2:1:1 ratio using interactive response technology (IRT) to receive double-blind study drug in one of the following treatment groups:

- Group 1: Upadacitinib 30 mg QD (N = 200) (Period 1) → Upadacitinib 30 mg QD (Period 2)
- Group 2: Upadacitinib 15 mg QD (N = 200) (Period 1) → Upadacitinib 15 mg QD (Period 2)
- Group 3: Placebo (N = 100) (Period 1) → Upadacitinib 30 mg QD (Period 2)
- Group 4: Placebo (N = 100) (Period 1) → Upadacitinib 15 mg QD (Period 2)

Randomization will be stratified by prior exposure to bDMARD (yes/no) and geographic region.

See Section 5.5.3 for details.

Study Drug Dispensing, Dosing, and Compliance

Study drug will be dispensed to subjects beginning at Baseline (Day 1) and as specified in Table 2 and Table 4. The first dose of study drug will be administered after all other Baseline (Day 1) procedures are completed. Subjects will maintain a dosing diary for all study drug administered outside of the study visit (i.e., at home) to capture dosing dates and times. At visits specified in Table 2 and Table 4, the site personnel will review and retain a copy of the dosing diary, returned study drug kits, and empty study drug packaging to verify compliance.

All relevant dosing information will be entered into the eCRF at each visit.

Refer to Section 5.5 for additional information.

Study drug may be shipped from the study site directly to the study subject's home due to study modifications related to a state of emergency or pandemic situation like COVID-19 if all the following criteria are met:

- Direct-to-patient (DTP) shipment of study drug is allowed by local regulations and the relevant ethics committee
- Subject agrees to have the study drug shipped directly to their home
- Shipments may also include other study supplies (e.g., drug dosing diaries, in-home urine pregnancy test kits). Instructions will be provided by AbbVie as to how a study site can initiate a DTP shipment using Marken, a global vendor selected by AbbVie to provide this service when necessary. Shipments of study drugs from the study site to a subject's home will be appropriately temperature controlled (qualified shipper or temperature monitoring) within the labeled storage conditions. Signature is required upon delivery; due to

COVID-19 related social distancing, this may be provided by the courier after delivery. Documentation of the shipment is to be retained by the clinical site.

- AbbVie will not receive subject identifying information related to these shipments, as the site will work directly with the courier.

The study site is responsible for meeting IRB/IEC reporting requirements related to DTP shipments of study drug, and for obtaining consent to provide delivery information to the courier and documenting this consent in source documents.

Optional Home Healthcare Service Due to State of Emergency or Pandemic Situation like COVID-19

Subjects may be offered the option of home healthcare visits provided by a study nurse or third-party vendor. Study procedures conducted in the home setting may include vital signs and body weight, physical exam, blood and urine samples collection, urine pregnancy test, adverse event and concomitant therapy assessment including compliance to contraception requirements if applicable, latent TB risk assessment form, review of subject dosing diary, TJC and SJC performed by the same independent joint assessor, if possible, to minimize variability.

This option can only be offered in countries and sites that comply with local regulatory and IRB/IEC requirements for homecare. Any pre-requisite submissions or notifications to the site IRB/IEC and local competent health authority should be made, and approvals must be obtained prior to implementation.

The investigator should be available via phone call if a consultation is necessary.

It is recommended that medical personnel entering a subject's home adhere to local health regulations during the COVID-19 pandemic, such as the use of Personal Protective Equipment (PPE), as required.

If the home visits will not be performed by site personnel, the site may be responsible for selecting a vendor, contracting with a vendor, and for ensuring continued compliance with the terms of the Clinical Study Agreement.

Individuals performing home visits need to be added to the delegation log.

5.3.1.2 Collection and Handling of In Vivo Pharmacodynamic Biomarker and Optional Samples for Exploratory Research and Validation Studies

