Period 1 will begin at the Baseline Visit (Day 1) and will end at the Week 12 Visit. At the Baseline Visit, subjects who meet all the inclusion criteria and none of the exclusion criteria described in Section 5.2.1 and Section 5.2.2 will be enrolled into the study and randomized to double-blind treatment. During this period of the study, subjects will visit the study site at Weeks 1, 2, 4, 8, and 12. A ± 3 day window is permitted around scheduled study visits. The last dose of study drug in Period 1 is taken the day prior to the Week 12 visit. Subjects who complete Period 1, but decide not to continue in Period 2 should complete a 30 day follow-up visit after the last dose of study drug.

Period 2 (Long-Term Extension Period [248 Weeks])

Period 2 will begin at the Week 12 visit after all assessments have been completed. During Period 2, subjects will have a study visit at Weeks 16, 20, 24, 36, 48, every 12 weeks through Week 240 and Week 260/PD. A ± 7 day window is permitted around scheduled study visits. At Week 24, if a subject fails to meet LDA criterion (LDA defined as CDAI ≤ 10) investigator should adjust the subject's background RA therapies.

Starting at Week 24 and thereafter, at least 20% improvement in BOTH TJC AND SJC is required to remain on study drug. Anyone who does not fulfill this criterion at 2 consecutive visits (starting at Week 24) (see Section 5.2.3.1) must be discontinued from study drug.

Starting with Amendment 6, all subjects will receive open-label upadacitinib 15 mg QD, including those currently on upadacitinib 30 mg QD.

Discontinuation of Study Drug and Continuation of Study Participation (Period 1 and Period 2)

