A Follow-Up Visit will occur approximately 30 days after the last dose of study drug to obtain information on any new or ongoing AE/SAEs, and to collect vital signs and clinical laboratory tests.

Subjects taking oral study drug will complete the 30 day-Follow-Up Visit when they have either:

- Completed the last visit of Period 1 (Week 12), but decided not to participate in Period 2; OR
- Completed the last visit of Period 2; OR
- Prematurely discontinued study drug and/or study participation. If a PD visit has already occurred, then the 30 day Follow-Up visit may be a telephone call if a site visit is not possible. The Follow-Up Visit is not applicable for subjects who discontinued study drug and continued study participation and completed at least one study visit at least 30 days after the last dose of study drug.

Protocol Modifications due to State of Emergency or Pandemic like COVID-19

Study visits may be impacted by a pandemic situation (including the COVID-19 pandemic) or any state of emergency. If visits cannot be conducted onsite due to travel restrictions or other pandemic-related reasons, virtual visits, visits at alternative locations, or changes in the visit frequency and timing of study procedures, among others may be performed. Additional details are provided in the subsequent sections. Every effort should be made to ensure the safety of subjects and site staff, while maintaining the integrity of the study.

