The central laboratory chosen for this study will provide instructions regarding the collection, processing, and shipping of these samples.

If travel restrictions or other changes in local regulations due to state of emergency or pandemic situation like COVID-19 prevent the subject from having blood drawn for laboratory testing at the study site, it is possible for the Investigator to arrange for subjects to have laboratory work done at a local lab, hospital, or other facility to ensure the safety assessments are conducted per protocol. Local lab results should be obtained along with reference ranges and kept within the subjects' source documentation. Local lab results should be reviewed by the investigator or designee as soon as possible and documented in the eCRF.

If laboratory samples cannot be obtained, study drug administration may be continued provided labs have been obtained within the prior 3 months, the investigator has reviewed the laboratory results and confirmed and discussed with the subject that there is no safety concern for the subject to continue use of the study drug in the absence of current lab results. The subject should be scheduled for laboratory draws as soon as feasible and no later than the next scheduled visit in order to continue the study drug administration.

If laboratory results are not available within the prior 3 months/two consecutive 12-week intervals, study drug dispensation is not allowed until the required laboratory tests are completed to ensure the safety assessments are conducted per protocol.

Blood samples will be obtained for the laboratory tests at visits specified in [Table 2](#) and [Table 4](#). Blood draws should be performed only after all clinical assessments and questionnaires (HAQ-DI, Patient's Assessment of Pain, etc.) and vital sign determinations are obtained.

For clinic visits where samples for serum chemistry tests are collected, subjects should be fasting (a minimum 8-hour fast) whenever possible. If a subject is not able to fast when necessary, due to unforeseen circumstances, the non-fasting status will be recorded in study source documentation.

Urine samples will be obtained for urinalysis testing at visits specified in [Table 2](#) and [Table 4](#). The central laboratory will be responsible for performing a macroscopic

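### The emergency rule for missed laboratory draws sets two unequal limits, 3 months and two 12-week intervals, for one dispensing decision, and the longer one conflicts with the 3-month condition for continued dosing

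*Protocol*

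**What the plan says.** The rule is in Protocol Section 5.3.1.1, under Clinical Laboratory Tests, and applies when a state of emergency or pandemic prevents blood being drawn at the site. The text takes four steps.

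- A substitute draw is allowed: "it is possible for the Investigator to arrange for subjects to have laboratory work done at a local lab, hospital, or other facility".
- If no sample can be obtained, "study drug administration may be continued provided labs have been obtained within the prior 3 months". The investigator must also have reviewed those results and confirmed with the subject that there is no safety concern.
- The make-up draw is due "as soon as feasible and no later than the next scheduled visit in order to continue the study drug administration".
- The dispensing bar then follows: "If laboratory results are not available within the prior 3 months/two consecutive 12-week intervals, study drug dispensation is not allowed". The slash is not explained.

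On timing, the same section says "Study drug will be dispensed to subjects beginning at Baseline (Day 1) and as specified in Table 2 and Table 4". Period 2 visits are at Weeks 16, 20, 24, 36 and 48, then "every 12 weeks through Week 240 and Week 260/PD" (Section 5.1), and "A ± 7 day window is permitted around scheduled study visits". The emergency provision in Section 5.1 adds virtual visits, alternative locations, "or changes in the visit frequency and timing of study procedures, among others may be performed", with no upper limit on a delay. No other emergency provision in the protocol limits the age of laboratory results.

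**The concern.** A threshold for withholding drug should have one value. Here the sentence that controls dispensing names two, and the longer is nearly twice the shorter. In an emergency, dispensing may take place without an on-site visit: Section 5.3.1 lists it among activities that can be done by phone or video, and Section 5.3.1.1 permits direct-to-patient shipment. The age-of-labs rule is then a main check on further supply to someone who has had no recent blood draw.

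The interruption criteria in Table 7 for haemoglobin, neutrophils, lymphocytes, transaminases, creatinine and CPK need laboratory values to operate. Where the two limits disagree, one site could withhold a JAK inhibitor and another could supply the next 12 weeks of it, each pointing to the same sentence.

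**Working it through.** **Inputs.** The two limits are those in the dispensing sentence of Section 5.3.1.1. Visit spacing and the ±7-day window come from Section 5.1, and dispensing and laboratory visits from Table 4.

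**1. Are the limits equal?**
- 3 calendar months = 89–92 days.
- Two 12-week intervals = 2 × 84 = 168 days.
- Difference: 168 − 92 = 76 to 168 − 89 = 79 days. Ratio: 168/92 = 1.83 to 168/89 = 1.89.

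One 12-week interval (84 days) is close to 3 months; two are not. The stated equivalence cannot be reproduced.

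**2. Which limit does the surrounding text support?** The condition for continued administration uses 3 months alone. The make-up deadline, on the 12-week schedule, falls when the last labs are 84 + 84 = 168 days old. That number matches the longer limit, but the sentence fixes when blood must be drawn and does not authorise dispensing on results of that age. The balance favours 3 months.

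**3. When do the limits give different answers?**

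| Situation | Age of last labs | 3-month limit | Two-interval limit |
|---|---|---|---|
| One missed draw, visit on time | 84 days | dispense | dispense |
| One missed draw, latest in-window visit | 84 + 7 + 7 = 98 days | withhold | dispense |
| One missed draw, visit delayed by the emergency | up to 167 days | withhold once past 89–92 days | dispense |
| Two missed draws, visits on time | 168 days | withhold | withhold |

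The conflict zone is about 93–167 days. Within the visit windows, labs at the first missed draw are 70–98 days old (84 ± 14), so the excess over 3 months is at most 98 − 92 = 6 to 98 − 89 = 9 days. Larger excesses need a visit delayed under the emergency provision.

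**4. Who could be affected?** SAP Appendix B places all subjects in Period 2 when the pandemic began. Protocol Section 5.5.5.2 has all subjects through Period 1 by September 2018. From 30 September 2018 to the synopsis date of 25 November 2020 is 787 days, or 112.4 weeks, so remaining subjects were at Week 12 + 112.4 ≈ 124 or later. SAP Appendix B also says Period 1 reporting was completed in 2017, which puts them later still: 31 December 2017 to the same date is 1,060 days, or 151.4 weeks, giving about Week 163. Either way they were on the 12-week schedule.

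**5. The last interval.** After a missed Week 240 draw, the next scheduled visit is Week 260. The Week 228 labs would then be 32 × 7 = 224 days old (210–238 with windows). The planned schedule with no missed draw already leaves 20 × 7 = 140 days between Weeks 240 and 260, so the added exposure is 224 − 140 = 84 days.

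**The case against.** The strongest reply is that the disputed case is already decided. If labs are over 3 months old when a draw is missed, the condition for continued administration fails. A site that dispensed under the longer limit would hand over drug that the preceding paragraph does not allow the subject to take. On this view the two-interval phrase merely describes the same stop in visit terms, since an on-time subject lacks labs within 3 months only after a second miss. The gap inside the windows is also small, and reaching it needs one visit a full week early, the next a full week late, and no successful local or home draw.

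Most of this stands. A reader might infer that the protocol leaves the choice between 3 months and 168 days open. It does not: the administration condition points to 3 months. What survives is narrower. The dispensing sentence, read literally, still offers a longer limit that contradicts that condition. Treating the slash as *or* does not cure it, because results missing from either period and results missing from both give different limits.

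A reader might also set the 224 days at Week 260 against 3 months and call it a large breach. That overstates it. The planned gap is already 140 days, Table 4 marks no dispensing at Week 260, and the instruction to draw as soon as feasible already applies.

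**Conclusion.** The concern holds as a contradictory safety threshold of low severity. One dispensing decision carries limits of 89–92 and 168 days. The administration condition shows that the shorter should govern, so the longer is the error. The practical conflict is confined to labs about 93–167 days old after a single missed draw, and to 6–9 days beyond 3 months when both visits are within their windows.

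This rests on reading 3 months as calendar months and on dispensing at the Table 4 visits. The documents do not say how often or how long visits were delayed, nor how often a missed draw went unreplaced, so no share of subjects can be estimated. Investigator review of the last results, the instruction in Section 5.3.1 to draw as close as possible to the scheduled visit, and the local and home options all reduce the risk.

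The point should not be read as touching the trial's results. Period 1 reporting was complete before the pandemic, and no endpoint or analysis depends on this rule.

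**What to change.** In Section 5.3.1.1, delete the slash and the two-interval phrase. State one limit, as a fixed number of days since the last reviewed results, for both administration and dispensing. Three months corresponds to 89–92 days. A longer figure, such as 98 days to cover the visit windows, would need the sponsor's medical justification.

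Say also that the limit is checked when a draw is missed and at each dispensing. Otherwise a subject supplied on time at 84 days would pass it 5–8 days later (89 − 84 and 92 − 84), and the next-visit deadline for the make-up draw would lose its meaning.

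As a minor addition, state that a make-up draw for a missed Week 240 sample must not wait until Week 260. Local and home draws are already permitted.

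The cost is protocol wording, in the next amendment or a site letter. The downside is an occasional local or home draw, or a short hold in dispensing, including for some visits that are late but still within their window.

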5.3.1.2.1 In Vivo Pharmacodynamic Biomarker Samples

Blood samples will be collected at the visits indicated in [Table 2](#) and [Table 4](#) and will be utilized to assess effects of upadacitinib inhibition on certain lymphocyte subsets, including but not limited to T (CD4+ and CD8+) cells, B (CD19+) cells, natural killer (NK) cells, and natural killer-T (NKT) cells.

The samples should be labeled and shipped as outlined in the study-specific laboratory manual.

5.3.1.2.2 Optional Samples for Exploratory Research and Validation Studies

In Period 1, subjects will have the option to provide samples for exploratory research and validation studies. Subjects may still participate in the main study even if they decide not to participate in this optional exploratory research/validation study.

Exploratory research can help to improve our understanding of how individuals respond to drugs and our ability to predict which subjects would benefit from receiving specific therapies. In addition, exploratory research may help to improve our understanding of how to diagnose and assess/monitor RA by assessing associations between disease characteristics, outcomes data, and biomarkers of interest.

Validation studies, including those related to the development of potential in-vitro diagnostic tests, may be carried out retrospectively in order to assess associations between events of interest (i.e., efficacy and/or safety events) and candidate biomarkers.

AbbVie (or people or companies working with AbbVie) will store the biomarker exploratory research/validation studies samples in a secure storage space with adequate measures to protect confidentiality. The samples will be retained while research on upadacitinib (or drugs of this class) or RA and related conditions continues, but for no longer than 20 years after study completion.

DNA Samples for Pharmacogenetic or Epigenetic Analyses

Whole blood samples for DNA isolation will be collected at the visits indicated in [Table 3](#) from each subject who consents to provide samples for exploratory/validation research. The procedure for obtaining and documenting informed consent is discussed in [Section 9.3](#).

Samples will be shipped frozen to AbbVie or a designated laboratory for DNA extraction and/or long-term storage or analyses. Instructions for the preparation and shipment of the pharmacogenetic and/or epigenetic research samples will be provided in a laboratory manual.

RNA Samples for Transcriptomic and/or Epigenetic Analyses

Whole blood samples for RNA isolation will be collected at the visits indicated in [Table 3](#) from each subject who consents to provide samples for exploratory/validation research. The procedure for obtaining and documenting informed consent is discussed in [Section 9.3](#).

Samples will be shipped to AbbVie or a designated laboratory for RNA extraction and/or long-term storage or analyses. Instructions for the preparation and shipment of the samples will be provided in a laboratory manual.

Serum and Plasma Samples for Systemic Analyses, Including but Not Limited to Proteomic and Metabolomic

Serum and plasma samples will be collected at the visits indicated in [Table 3](#) from each subject who consents to provide samples for exploratory/validation research. The procedure for obtaining and documenting informed consent is discussed in [Section 9.3](#).

Samples will be shipped to AbbVie or a designated laboratory for long-term storage and/or analyses. Instructions for the preparation and shipment of the samples will be provided in a laboratory manual.

